#### **11.2.1.3 Adverse Events by Maximum Severity**

TEAEs will be summarized by maximum severity. If a subject has an AE with an unknown severity, then the subject will be counted in the severity category of unknown, even if the subject has another occurrence of the same event with a severity present. The only exception is that if the subject has another occurrence of the same AE with the most extreme severity (severe). In this case, the subject will be counted under the severe category.

#### **11.2.1.4 Adverse Events by Maximum Relationship**

TEAEs will be summarized by maximum relationship to study drug, as assessed by the investigator. If a subject has an AE with an unknown relationship, then the subject will be counted in the relationship category of "unknown," even if the subject has another occurrence of the same event with a relationship present. The only exception is if the

---

subject has another occurrence of the same AE with a relationship assessment of reasonable possibility in which case, the subject will be counted under reasonable possibility category.

**11.2.1.5 Frequent ( $\geq 5\%$ ) Adverse Events and Reasonably Possibly Related Adverse Events by System Organ Class and Preferred Term**

TEAEs and reasonably possibly related AEs occurring for more than 5% of the subjects in any treatment groups will be summarized by MedDRA PT in decreasing frequency separately.

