6.1.3 Relationship to Study Drug

The investigator will use the following definitions to assess the relationship of the AE to the use of study drug:

Reasonable Possibility	After consideration of factors including timing of the event, biologic plausibility, clinical judgment, and potential alternative causes, there is sufficient evidence (information) to suggest a causal relationship.
-------------------------------	---

No Reasonable Possibility After consideration of factors including timing of the event, biologic plausibility, clinical judgment, and potential alternative causes, there is **insufficient** evidence (information) to suggest a causal relationship

For causality assessments, events assessed as having a reasonable possibility of being related to the study drug will be considered "associated." Events assessed as having no reasonable possibility of being related to study drug will be considered "not associated." In addition, when the investigator has not reported a causality or deemed it not assessable, AbbVie will consider the event associated.

[figure not shown]
If an investigator's opinion of no reasonable possibility of being related to study drug is given, an Other cause of event must be provided by the investigator for the serious adverse event.

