8.1.6 Safety Analysis

8.1.6.1 General Considerations

Safety analyses will be carried out using the Safety Population, in each period, and is based on treatments actually received. Safety will be assessed by AEs, physical examination, laboratory assessments, ECG, and vital signs. Frequency tables and lists of subjects with treatment-emergent AEs by preferred term as in the Medical Dictionary for Regulatory Activities (MedDRA) dictionary, by system organ class, by severity, and by relationship to the study drug as assessed by the Investigator will be provided. The changes from baseline in vital signs, physical examination results, and clinical laboratory values will be analyzed in a descriptive manner. Shift of laboratory values from baseline to defined time points will be tabulated.

Missing safety data will not be imputed.

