8.1.6.2 Analysis of Adverse Events

8.1.6.2.1 Treatment-Emergent Adverse Events (TEAE)

AEs will be coded using MedDRA. A TEAE is defined as an AE that began or worsened in severity after initiation of study drug.

AEs starting more than 30 days following the last dose of study drug will not be included in summaries of TEAEs.

As a general safety summary, the number and percentage of subjects experiencing TEAEs will be summarized for each treatment group for the following AE categories:

- All AEs;
- All severe AEs;
- All reasonably possibly related AEs;
- All SAEs;
- Frequent AEs (reported in 5% of subjects or more in any treatment group);
- Frequent reasonably possibly related AEs (reported in 5% of subjects or more in any treatment group);
- Discontinuations due to AEs;
- Death.

TEAEs will also be summarized separately for the period when subjects receive ABT-494 monotherapy, the period when subjects receive concomitant mometasone furoate, and the period when subjects receive concomitant triamcinolone acetonide.

Additional AEs may be considered for tabulation/summary based on recommendations from Clinical and Safety as deemed appropriate.

TEAEs will be summarized and presented by system organ classes (SOCs) and preferred terms (PTs) using MedDRA. The SOCs will be presented in alphabetical order, and the PTs will be presented in alphabetical order within each SOC.

TEAE will also be summarized by maximum severity and by maximum relationship.

- The AEs of special interest (including but not limited to serious infections, opportunistic infections, malignancy, hepatic disorder, gastrointestinal perforations, anemia, neutropenia, herpes zoster, creatine phosphokinase (CPK elevation), decreased lymphocyte counts, renal dysfunction, tuberculosis, adjudicated cardiovascular events, cardiac arrhythmias) will be summarized. Event rate (per 100 patient years) for AEs of special interest will also be summarized for the combined safety analysis of Period 1 and Period 2.

All AEs leading to discontinuation will be presented in listing format. A listing by treatment group of TEAEs grouped by SOC and MedDRA preferred term with subject identification numbers will be generated.

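### SAP adverse-event counting rules on missing causality and on the 5% cut-off do not match the protocol, and SAP 12.1 declares neither difference

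*SAP*

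**What the plan says.** **Causality.** Protocol 6.1.3 gives the investigator two ratings, reasonable possibility and no reasonable possibility. It then covers the remaining case: "when the investigator has not reported a causality or deemed it not assessable, AbbVie will consider the event associated".

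SAP 11.2.1.4 opens with "TEAEs will be summarized by maximum relationship to study drug, as assessed by the investigator". It continues: "If a subject has an AE with an unknown relationship, then the subject will be counted in the relationship category of" unknown, even if another occurrence of the same event has a rating. The one exception is that the "subject has another occurrence of the same AE with a relationship assessment of reasonable possibility in which case" the subject is counted as related. SAP 11.2.1.1 lists overview rows for related TEAEs and related TESAEs and does not say how a missing rating is handled there.

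**Frequency cut-off.** Protocol 8.1.6.2.1 asks for "Frequent AEs (reported in 5% of subjects or more in any treatment group") and uses the same cut-off for frequent related events. The heading of SAP 11.2.1.5 also says at least 5%. The sentence below it reads "TEAEs and reasonably possibly related AEs occurring for more than 5% of the subjects in any treatment groups".

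**Declared changes.** SAP 12.1 lists four changes from the protocol: baseline tests, the quadratic model, DLQI and the pruritus responder endpoint. Neither counting rule is among them.

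**The concern.** These are working instructions to programmers. If the SAP text is followed literally, an event that the protocol has the sponsor treat as associated is tabulated in a third class that the protocol's scale does not contain. The overview rows and the frequent related-event table have no line for that class, so the event has no place in them. The cut-off sentence gives a programmer an instruction that conflicts with the heading above it. At the planned arm size the boundary falls exactly on a whole number of subjects. Both differences run in the same direction, towards fewer events shown as related or frequent. In arms this small, one subject can change a row.

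**Working it through.** The plan states no figure on this point, so there is none to reproduce.

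**1. Causality: the two rules side by side, for one subject and one preferred term**

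| Ratings across occurrences | SAP 11.2.1.4 | Protocol 6.1.3 applied |
|---|---|---|
| Any reasonable possibility | related | related |
| Missing or not assessable only | unknown | related |
| Missing plus no reasonable possibility | unknown | related |
| No reasonable possibility only | not related | not related |

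The SAP does not define unknown. Since the protocol's scale has only two ratings, I take it to mean unreported or not assessable. Every subject in the unknown row would then be related under 6.1.3. For a given preferred term a reader can recover that count by adding the two rows of the maximum-relationship table. The overview rows and the frequent related-event table do not allow this.

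Size: one subject moves a rate by 1/40 = 2.5 points in Period 1. In Period 2 it is 1/20 = 5 points, assuming 40 split 1:1 with no dropout. The total effect cannot be computed, because no rate of missing causality is given.

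**2. Cut-off: when the two wordings differ**

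Inputs: 40 per arm (protocol synopsis and 8.2); 1:1 re-randomization (protocol 5.1); eight Period 2 groups (SAP Table 1).

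The rules differ only for a count x with x/n exactly 1/20, that is n = 20x. So n must be a multiple of 20.

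| Group size | Minimum count, at least 5% | Minimum count, more than 5% |
|---|---|---|
| 19 | 1 | 1 |
| 20 | 1 | 2 |
| 21 | 2 | 2 |
| 39 | 2 | 2 |
| 40 | 2 | 3 |
| 41 | 3 | 3 |

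**3. How often the listing would change**

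Both documents list an event that reaches the cut-off in any treatment group. The rules therefore disagree when at least one arm sits exactly on the boundary and no arm exceeds it. For a independent arms with a common true rate and boundary count k:

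P(disagree) = F(k)^a − F(k−1)^a, where F is the binomial distribution function.

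- Four arms of 40, rate 5%, k = 2. P(X ≥ 2) = 0.601 and P(X ≥ 3) = 0.323, so F(1) = 0.399 and F(2) = 0.677. Then 0.677^4 − 0.399^4 = 0.210 − 0.025 = 0.18.
- Eight arms of 20, rate 5%, k = 1. P(X ≥ 1) = 0.642 and P(X ≥ 2) = 0.264, so F(0) = 0.358 and F(1) = 0.736. Then 0.736^8 − 0.358^8 = 0.086 − 0.0003 = 0.086, about 9%.
- Four arms of 40, rate 3%. The chance that any arm reaches the cut-off is 0.808 with at least 5% and 0.394 with more than 5%, a difference of 0.41.

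**The case against.** **The SAP follows the protocol's analysis text.** Protocol 8.1.6.1 says tables "by relationship to the study drug as assessed by the Investigator will be provided" and that missing safety data are not imputed. SAP 6.0 and 11.1 repeat the second point. On this view 6.1.3 governs how the sponsor classifies an event, not how an investigator-assessed table is built. This stands in part: the protocol does not expressly apply 6.1.3 to this table, so a reader who infers a flat contradiction goes too far. But 6.1.3 is the protocol's only specific rule for these events, and not assessable is something an investigator reports rather than a missing value. The tension needs a stated resolution.

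**Nothing is hidden.** A reader might infer that related and frequent events are under-reported. The documents do not support that as a general statement. Unknown outranks no reasonable possibility, so these subjects are never counted as unrelated. SAP 11.2.1.2 tabulates every TEAE with no cut-off. That events leave the overview rows is also an inference from the SAP's silence.

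**The cut-off is a wording slip.** The SAP heading and table of contents agree with the protocol, so a deliberate change is unlikely. That stands, but the sentence is what would be programmed. Group sizes need not be exactly 40 or 20: enrolment is approximate, safety groups are as treated, and only Period 1 completers are re-randomized.

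**Single-arm probabilities overstate the effect.** At a true rate of 5%, one arm of 40 has exactly 2 events with probability 28%, and one arm of 20 has exactly 1 with probability 38%. A reader might take these as the chance of an event being dropped. They are not, because an event over the cut-off in any other arm is still listed.

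**Severity is a different matter.** SAP 11.2.1.3 says that with an unknown grade "then the subject will be counted in the severity category of unknown, even if the subject has another occurrence of the same event", unless another occurrence is severe. A reader might count this as a third conflict. The protocol has no rule for unknown severity, and this rule does not touch related or frequent counts.

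**Conclusion.** Both differences stand as undeclared inconsistencies worth correcting, in a limited form.

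On causality, SAP 11.2.1.4 departs from protocol 6.1.3 and sits in unresolved tension with 8.1.6.1. The probable result is a lower count in the related rows and in the frequent related-event table, by 2.5 points per subject in an arm of 40. The total could be zero, since no rate of missing causality is given.

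On the cut-off, SAP 11.2.1.5 is inconsistent within itself, and its sentence conflicts with the protocol. The listing changes only where a group size is a multiple of 20. The figures of about 18% (four arms of 40) and about 9% (eight arms of 20) assume exactly those sizes, independent arms and a true rate of 5% in each. Only membership of the frequent-event tables is at stake. No efficacy endpoint is affected.

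**What to change.** - **SAP 11.2.1.1, 11.2.1.4 and 11.2.1.5:** count missing or not-assessable causality as reasonable possibility, as in protocol 6.1.3, with a footnote giving the number so assigned. Alternatively, keep the unknown class and declare and justify the departure in SAP 12.1.
- **SAP 11.2.1.5:** change the sentence to 5% or more, to match its heading and protocol 8.1.6.2.1.
- **Optional, SAP 11.2.1.3:** report the highest known severity and footnote the unknowns. This is an internal improvement and is not needed for agreement with the protocol.

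The cost is a few SAP sentences and small program edits. The reported related and frequent counts may become slightly less favourable.

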**11.2.1.6 Adverse Events of Special Interests**

The AESI categories will be identified by the following search criteria per Standard MedDRA Queries (SMQs)/Company MedDRA Queries (CMQs) specified in [Table 15](#).

**Table 15. AESI for Upadacitinib with SMQs/CMQs Searches**

AESI	Type of MedDRA Query	Broad or Narrow Search	SMQ/CMQ Search Criteria
Serious Infections	CMQ		"Infections" – Subset for SAEs
Opportunistic Infection	CMQ		"Opportunistic Infection"
Malignancy	SMQ	Narrow	"Malignancies"
Non-Melanoma Skin Cancer (NMSC)	SMQ	Broad	Skin Malignant tumours (Broad SMQ) removing Melanoma CMQ
Malignancy excluding NMSC			Malignancy Narrow SMQ and removing NMSC output
Lymphoma	SMQ		"Malignant Lymphomas"
Hepatic Disorder	SMQ	Narrow	"Drug Related Hepatic Disorders"
Gastrointestinal Perforations	SMQ	Narrow	"Gastrointestinal Perforation"
Anemia	CMQ		"Non-Hemolytic and Non-Aplastic Anemias"
Neutropenia	CMQ		"Hematological Toxicity – Neutropenia"
Lymphopenia	CMQ		"Hematological Toxicity – Lymphopenia (Veliparib Product Specific)"
Herpes Zoster	CMQ		"Herpes Zoster"
Rhabdomyolysis/myopathy	SMQ	Narrow	"Rhabdomyolysis/Myopathy"
Creatine Phosphokinase (CPK Elevation)	PT		Search only for the PT of "Blood creatine phosphokinase increased"
Renal Dysfunction	SMQ	Narrow	"Acute Renal ,Failure"
Tuberculosis	CMQ		"Tuberculosis"
Adjudicated cardiovascular events a	Output from CAC		
Cardiac Arrhythmias	SMQ	Narrow	"Torsade de pointes/QT Prolongation" "Tachyarrhythmias"

a. Reviewed and adjudicated by an independent Cardiovascular Adjudication Committee in a blinded manner.

Additional AEs may be considered for tabulation/summary based on recommendations from Clinical and Safety as deemed appropriate.

### **11.2.1.7 Adverse Events by 100 Patient Years**

TEAEs will be summarized by event rate per 100 subject years, defined as

$$100 * (\text{Number of TEAEs}) / (\text{Total Patient Years})$$

where total patient years is defined as the sum of the study drug exposure (defined in Section 9.1) of all subjects normalized by 365.25, and rounded to 1 decimal place. Event rate (per 100 patient years) for AEs of special interest will also be summarized for the combined safety analysis of Period 1 and Period 2.

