#### **Period 1:**

For subjects who did not continue into Period 2:

- Date of last dose of study drug in Period 1 – Date of first dose of study drug in Period 1 + 1.

For subjects who continued into Period 2: the minimum of

- Date of first dose of study drug in Period 2 – Date of first dose of study drug in Period 1.
  - Date of last dose of study drug in Period 1 – Date of first dose of study drug in Period 1 + 1.
-

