### **Period 2:**

- Date of last dose of study drug in Period 2– Date of first dose of study drug in Period 2 + 1.
- For interim analysis at Week 32, minimum of the above and (cutoff date – Date of first dose of study drug in Period 2 + 1).

Additional summaries of upadacitinib exposures by dose level will also be performed including exposure to each dose level across periods.

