### **11.2.1 Treatment-Emergent Adverse Events**

A treatment-emergent Adverse Event (TEAE) is defined as an adverse event with an onset or worsening date that is on or after the first dose of study drug, and no more than 30 days after the last dose of study drug.

AEs where the onset date is the same as the study drug start date are assumed to be treatment-emergent. If an incomplete onset date was collected for an adverse event, the event will be assumed to be treatment-emergent unless there is other evidence that confirms that the event was not treatment-emergent (e.g., the event end date was prior to the study drug start date).

TEAEs for the safety population in each period are defined as an event with a start date on or after the date of first study drug dose in each period and up to 30 days after the last dose of study drug in the analysis period, or prior to the date of first dose in the subsequent period for subjects who entered in to the subsequent period.

Adverse event data will be coded using the Medical Dictionary for Drug Regulatory Activities (MedDRA) version 20.0 or most up to date version.

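### Adverse event rates per 100 patient-years count events up to 30 days after the last dose but divide by time to the last dose only, which in Period 1 inflates arms unequally when discontinuation differs

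*SAP*

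**What the plan says.** **Events counted.** SAP 11.2.1 defines a treatment-emergent event as one starting or worsening on or after the first dose "and no more than 30 days after the last dose of study drug". For the by-period summaries the window runs "up to 30 days after the last dose of study drug in the analysis period" or, for those who continue, "prior to the date of first dose in the subsequent period for subjects who entered in to the subsequent period". Protocol 8.1.6.2.1 has the same limit: "AEs starting more than 30 days following the last dose of study drug will not be included in summaries of TEAEs".

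**Time counted.** SAP 11.2.1.7 gives the rate as 100 times the number of such events over total patient-years, "where total patient years is defined as the sum of the study drug exposure", with exposure taken from SAP 9.1 and divided by 365.25. SAP 9.1 gives exposure for a subject who does not continue as "Date of last dose of study drug in Period 1 – Date of first dose of study drug in Period 1 + 1", and for Period 2 as "Date of last dose of study drug in Period 2– Date of first dose of study drug in Period 2 + 1". Neither formula extends past the last dose. Protocol 8.1.3.3 defines exposure in the same way.

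Nothing in either document adds the 30 days to patient-years or limits the events in the rate to those with onset on drug.

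**The concern.** A rate per patient-year should count events and time over the same window. Here a subject who stops at Day 28 of Period 1 can contribute events over as many as 58 days (28 + 30) but only 28 days of person-time. A subject who continues into Period 2 has almost no such gap, because the Period 1 window closes at the first Period 2 dose.

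The tail events are likely to be captured. Subjects who stop drug are asked to keep attending visits, and a contact about 30 days after the last dose is planned (Protocol 5.1 and 5.4.1).

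The rates are a planned safety output (Protocol synopsis; SAP 11.2.1.7), and Period 1 is the comparison of all three doses with placebo as first randomised. Exposure adjustment is meant to remove the effect of unequal time at risk. As defined, it leaves an error that grows with discontinuation.

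**Working it through.** The documents give no adverse event rates and no discontinuation rates by arm, so there is no stated figure to reproduce.

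**Inputs from the documents**
- Period 1 lasts 16 weeks = 112 days; Period 2 lasts 72 weeks = 504 days (Protocol 5.1).
- The tail is 30 days (SAP 11.2.1).
- Planned arm size is 40 (SAP 4.3).

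**Assumed inputs**
- d: share who stop and do not enter Period 2.
- t: their mean days on drug.
- k: off-drug event rate divided by on-drug rate.
- A constant event rate while on drug, and the full 30 days of follow-up after stopping.

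**Period 1.** Only those who stop carry the tail:

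inflation = 1 + 30·k·d / [(1 − d)·112 + d·t]

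With t = 56 and k = 1:
- d = 10%: 100.8 + 5.6 = 106.4 days per subject; 3/106.4 = 2.8%.
- d = 30%: 78.4 + 16.8 = 95.2 days; 9/95.2 = 9.5%.
- d = 40%: 67.2 + 22.4 = 89.6 days; 12/89.6 = 13.4%.

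| d | t = 28 to 84, k = 1 | t = 56, k = 0.5 |
|---|---|---|
| 5% | about 1.4% | 0.7% |
| 10% | 2.7–2.9% | 1.4% |
| 30% | 8.7–10.4% | 4.7% |
| 40% | 11.9–15.3% | 6.7% |

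At k = 0 there is no inflation.

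**Between arms, with truly equal rates (t = 56, k = 1).** At 30% against 10%, 1.0945/1.0282 = 1.06. At 40% against 10%, 1.1339/1.0282 = 1.10. The arm with more stopping shows a spurious excess of 6% or 10%.

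**As rates.** Take 40 subjects per arm and an illustrative true rate of 300 per 100 patient-years.
- d = 10%: 40 × 106.4/365.25 = 11.65 patient-years on drug, plus 40 × 0.1 × 30/365.25 = 0.33 in the tail. Events are 3 × 11.98 = 35.9. The SAP rate, with patient-years rounded to 11.7, is 307.
- d = 40%: 9.81 plus 1.31 patient-years, 33.4 events. The SAP rate, with patient-years rounded to 9.8, is 341.
- Dividing by on-drug time plus tail gives 300 in both arms.

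**Period 2.** No dosing period follows, so completers carry the tail as well:

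inflation = 1 + 30·k / [(1 − d)·504 + d·t]

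With k = 1 this is 30/504 = 6.0% at d = 0. For t = 84 to 252 it is 7.0–7.9% at d = 30% and 7.9–10.2% at d = 50%.

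**Both periods combined (112 + 504 = 616 days).** Following subjects by Period 1 arm, with stopping at Day 56 and none in Period 2:
- d = 30%: 0.7 × 616 + 0.3 × 56 = 448 days; 30/448 = 6.7%.
- d = 10%: 0.9 × 616 + 0.1 × 56 = 560 days; 30/560 = 5.4%.
- Spurious excess between arms: 1.067/1.054, about 1.3%.

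**The case against.** Several points on the other side stand.

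- **Size.** The illustrative stopping rates have no source in the documents and may be too high. With the planning figures for placebo (mean improvement 35, SD 40; SAP 4.3), a normal approximation puts worsening of 25% or more at z = (−25 − 35)/40 = −1.5, or 6.7% of placebo subjects at one visit. The mandatory Period 1 stop needs two consecutive visits. At d = 7% and t = 56 the inflation is 2.1/108.1 = 1.9%. This applies Week 16 figures to Weeks 4 to 12 and ignores other reasons for stopping, so it shows that the effect may be small but does not cap it.
- **Follow-up.** Thirty days is a maximum. After withdrawal of consent, the follow-up contact depends on the subject's willingness.
- **Consequence.** The main adverse event tables give numbers and percentages of subjects, which use no person-time. SAP 11.1 plans between-group comparisons only for laboratory and vital sign changes. With about 35 events in an arm, the Poisson relative standard error is 1/√35, about 17%, which exceeds the distortion in the scenarios above.
- **Remedy.** Longer patient-years are not neutral. The half-life is 9 to 14 hours (Protocol 3.0), and subjects who stop are then followed on standard of care (Protocol 5.4.1). Off-drug time can dilute a real drug effect.

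A reader might infer that the rule makes upadacitinib look safer. The documents do not support that. The planning assumptions (35% improvement on placebo, 70% on 30 mg) make more stopping on placebo for lack of efficacy plausible. If adverse events cause more stopping on 30 mg, however, the same rule inflates the drug's rate.

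A reader might also infer that the arm with most discontinuation is always inflated most. That is chiefly a Period 1 result and needs similar stopping times: 20% stopping at a mean of Day 10 gives 6.6%, while 22% at Day 100 gives 6.0%.

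**Conclusion.** The mismatch is explicit in the SAP, and rates produced as written will include events that fall outside the person-time counted.

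In Period 1 the error depends on discontinuation, and differs between arms if discontinuation does. It is roughly 3% at 10% stopping and 9 to 13% at 30 to 40%, given an equal off-drug event rate, full 30-day follow-up and stopping at Day 56. It shrinks in proportion if the off-drug rate is lower. The direction of any active-versus-placebo distortion cannot be stated in advance.

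In Period 2 all arms are raised by about 6% or more, and the difference between arms there and in the combined analysis is small. Subject counts and percentages are not affected. This is a minor point, worth correcting because it is simple to correct.

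**What to change.** In SAP 11.2.1.7, stop using SAP 9.1 exposure as the denominator. Define patient-years for these rates from the first dose to the earliest of the last dose plus 30 days, the first dose of the next period, or the last contact. At the Week 32 interim, also cap at the data cutoff, as SAP 9.1 already does for exposure. Beside this rate, show a companion that counts only events with onset between first and last dose, divided by SAP 9.1 exposure.

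The cost is one SAP definition and a change to the safety programming, using dates already collected. The rates become slightly lower, and their patient-years will no longer match the exposure table, which needs a footnote. Including off-drug time can dilute a drug effect if the off-drug rate is lower; the on-drug companion rate shows whether that has happened.
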